**Table 8.1.3-2: Observed ORR with Exact 95% CI**

Sample Size	Number of Responses	ORR	95% Exact CI
90	18	20%	[12.3%, 29.8%]
	27	30%	[20.8%, 40.6%]
	32	36%	[25.7%, 46.4%]
	37	41%	[30.8%, 52.0%]
	46	51%	[40.4%, 61.8%]
100	20	20%	[12.7%, 29.2%]
	30	30%	[21.2%, 40.0%]
	35	35%	[25.7%, 45.2%]
	40	40%	[30.3%, 50.3%]
	50	50%	[39.8%, 60.2%]
120	24	20%	[13.3%, 28.3%]
	36	30%	[22.0%, 39.0%]
	42	35%	[26.5%, 44.2%]
	48	40%	[31.2%, 49.3%]
	60	50%	[40.7%, 59.3%]

### **8.1.4 Melanoma Prior IO Extended Expansion (Part D)**

The objective of this expansion in melanoma subjects whose disease is progressing while receiving anti-PD-1 (anti-PD-L1 allowed in Part D2) antibody therapies is to assess safety and tolerability of more convenient dosing regimen (ie, coadministration and Q4W dosing interval) and demonstrate preliminary clinical evidence of the treatment effect measured by ORR, as determined by BICR, that may represent substantial improvement over available therapies in subjects with LAG-3 expression (Part D1).

#### **8.1.4.1 Melanoma Prior IO Extended Expansion (Part D1-Q2W)**

Data from Part C melanoma subjects who progressed while receiving anti-PD-1 antibody therapies demonstrated a preliminary evidence that subjects with LAG-3 expression are more likely to respond to treatment of BMS-986016 in combination with nivolumab. The marker prevalence using the initial 1% cut (ie, LAG-3 expression  $\geq 1\%$ ) is estimated to be approximately 60% in this patient population.

In order to establish safety and tolerability of a more convenient dosing regimen and further characterize an enriched responder population, approximately a total of 150 subjects who meet the eligibility criteria for Part D1 will be treated with BMS-986016 80 mg + nivolumab 240 mg Q2W coadministered. A sample size of 150 is expected to provide approximately 90 subjects with LAG-3 expression using the initial cutoff of 1% and provide reasonable precision to examine the enrichment of patient population with LAG-3 expression.

Since the optimal marker cutpoint is not well known prior to the study, several different cutoffs may be explored, and, depending on the prevalence of the marker-positive using these cutoffs, the

initial total sample size may be modified in order to have an adequate precision for demonstrating preliminary clinical evidence of the treatment effect in the marker-positive population (ie, approximately 90 subjects). Although evaluation of the cutpoint will be based on the ORR, the decision of the cutpoint will be based on the totality of the efficacy data, including DOR and DCR.

Additionally, in an effort to explore an enriched patient population in advanced melanoma subjects who progressed while on anti-PD-1 antibody therapies in Part D1, other potential predictive markers such as BRAF mutation status may be explored. Approximately 60 subjects among the 90 subjects with LAG-3 expression in Part D1 are expected to be BRAF wild-type.

For the purpose of demonstrating preliminary clinical evidence of the treatment effect, the primary efficacy population will be subjects with LAG-3 expression who progressed while on anti-PD-1 antibody therapies and receive BMS-986016 80 mg + nivolumab 240 mg Q2W in Part D1. A portion of subjects in Part C who meet the eligibility criteria of Part D1 will be included in a sensitivity analysis to further strengthen the evidence.

The sample size of 90 subjects with LAG-3 expression was determined based on the ability to produce a CI, which would exclude an ORR of the historic response, and to provide sufficient information for a reliable understanding of the safety profile.

There is no standard of care for advanced melanoma patients who have progressed during prior anti-PD-1 therapy; thus, the demonstration of effective and tolerable therapy in these patients remains a large unmet need. The only published or reported studies in this clinical setting employ anti-CTLA-4 therapy, namely ipilimumab, and they are small retrospective or exploratory ad hoc analyses. The patient population characteristics and results of ipilimumab monotherapy in these studies are listed in Table 8.1.4.1-1 below. There have been no prospective studies defining the benefit of anti-CTLA-4 therapy after progression during anti-PD1 therapy.

**Table 8.1.4.1-1: Ipilimumab After Prior Anti-PD-1 Therapy**

Study Population	ORR/CI/DOR	Toxicity	Source
Retrospective: Sequential treatment of anti-PD-1 (all progressed on clinical trials) then ipilimumab. 10% BRAF mutant. 42% with PD as BOR to prior anti-PD-1. 10% prior ipilimumab (response not reported).	10% (4/40 PRs) No CI reported DOR not reported	55% received all 4 doses of ipilimumab 35% had Grade 3 to 5 irAE; 1 drug-related death due to pneumonitis	Bowyer et al 10.1038/bjc.2016.10 7
Retrospective: Documented progression on prior anti-PD-1 as per RECIST v1.1 (details not provided). 15% BRAF mutant. 51% with PD as BOR to prior anti-PD-1. 26% prior ipilimumab (response not reported).	16% (7/43 PRs) No CI reported DOR not reported Median DoDC 7 months 95% CI (2.8-22.8) months	53% received all 4 doses of ipilimumab (33% did not due to toxicity) Rates of irAEs were not reported	Zimmer et al 10.1016/j.ejca.2017.01 .009
Exploratory post-hoc analysis of patients who received ipilimumab sequentially after pembrolizumab	13% (3 CRs and 10 PRs out of 97 patients) No CI reported	Not reported	Long et al KEYNOTE-006 presentation at

**Table 8.1.4.1-1: Ipilimumab After Prior Anti-PD-1 Therapy**

Study Population	ORR/CI/DOR	Toxicity	Source
(91% with documented progression). Data from subsequent therapies case report forms. 16% BRAF mutant. 62% with PD as BOR to prior anti-PD1.	DOR not reported		Society for Melanoma Research November 6-9, 2016
All treated subjects - nivolumab crossover to ipilimumab (the subjects randomized to nivolumab who received ipilimumab as subsequent therapy). 56% with PD as BOR to prior anti-PD-1.	10% (7/68 PRs) 95% CI (4.2%, 20.1%) DOR not reported	Not reported	CA209066 study Unpublished analysis

Combined analyses employing a standard response evaluable population definition across the multiple small studies of ipilimumab monotherapy in the setting of prior anti-PD-1 therapy reveal an approximate 12% ORR. Durability of these responses are poorly documented.

In heavily pretreated patients where clinical benefit is observed in only a subset of the population, safety is a significant concern. The reported rates of Grade 3 (or greater) TRAEs of approximately 35% from single-agent ipilimumab after anti-PD-1 therapy limits the overall utility of this approach.

The majority of our patient population (approximately 60%) have also been previously treated with anti-CTLA-4 therapy. There are no reported effective therapies in this setting. In addition, antitumor responses with continued anti-PD-1 therapy after initial progression on anti-PD-1 therapy is relatively rare, with estimates of incidence of approximately 5%. Thus, given a population in which all have progressed during prior anti-PD-1 therapy, and the majority have received prior anti-CTLA-4 therapy as well, it is reasonable to target an ORR that excludes 10% as a lower bound within a 95% CI.

**Table 8.1.4.1-2: Observed ORR with Exact 95% CI for Cohort D**

Sample Size	Number of Responses	ORR	95% Exact CI
60	12	20%	[10.8%, 32.3%]
	15	25%	[14.7%, 37.9%]
	18	30%	[18.9%, 43.2%]
90	16	18%	[10.5%, 27.3%]
	18	20%	[12.3%, 29.8%]
	20	22%	[14.1%, 32.2%]
120	20	17%	[10.5%, 24.6%]
	24	20%	[13.3%, 28.3%]
	27	23%	[15.4%, 31.0%]

**Table 8.1.4.1-2: Observed ORR with Exact 95% CI for Cohort D**

Sample Size	Number of Responses	ORR	95% Exact CI
150	24	16%	[10.5%, 22.9%]
	27	18%	[12.2%, 25.1%]
	30	20%	[13.9%, 27.3%]
220	26	12%	[7.9%, 16.8%]
	29	13%	[9.0%, 18.4%]
	32	15%	[10.2%, 19.9%]

**8.1.4.2 Melanoma Prior IO Focused Eligibility Expansion (Part D1-Q4W)**

The coprimary objective in Part D1-Q4W is to evaluate the difference in safety between coadministration relative to FDC as measured by the incidence of AEs in the Broad Scope MedDRA Anaphylactic Reaction SMQ occurring within 2 days after dosing during the combination and to confirm with Q4W dosing of BMS-986016 160 mg in combination with nivolumab 480 mg the safety of the BMS-986016 80 mg in combination with nivolumab 240 mg Q2W in advanced melanoma subjects who progressed while on anti-PD-1 antibody therapies (see [Appendix 5](#)).

Prior to Revised Protocol 09, subjects are being enrolled into a single arm: Part D1 BMS-986016 80 mg + nivolumab 240 mg Q2W. Subsequent to this amendment, and until the enrollment to Part D1 BMS-986016 80 mg + nivolumab 240 mg Q2W is completed, subjects in Part D1 will be randomized 1:1:1 to Part D1 BMS-986016 80 mg + nivolumab 240 mg Q2W, Part D1 BMS-986016 160 mg + nivolumab 480 mg Q4W coadministration, and Part D1 BMS-986213 (relatlimab 160 mg/nivolumab 480 mg) Q4W arms. Once enrollment to Part D1 BMS-986016 80 mg + nivolumab 240 mg Q2W is completed, subjects will be randomized 1:1 to Part D1 BMS-986016 160 mg + nivolumab 480 mg Q4W coadministration and Part D1 BMS-986213 (relatlimab 160 mg/nivolumab 480 mg) Q4W arms. If enrollment to Q4W arms is completed prior to arm BMS-986016 80 mg + nivolumab 240 mg Q2W, then enrollment to arm BMS-986016 80 mg + nivolumab 240 mg Q2W will be completed as a single arm.

Approximately 150 subjects will be randomized to the 2 treatment arms Part D1 BMS-986016 160 mg + nivolumab 480 mg Q4W coadministration and Part D1 BMS-986213 (relatlimab 160 mg/nivolumab 480 mg) Q4W. This number of treated subjects was chosen to achieve a sufficient level of precision for a descriptive analysis to estimate the difference in rates of AEs in the Broad Scope MedDRA Anaphylactic Reaction SMQ between the 2 treatment arms. Seventy-five (75) treated subjects per arm will allow estimation of the rate difference within 95% confidence limits of  $\pm 15\%$  or less and will be supplemented by a qualitative clinical assessment of the type and severity of events to evaluate benefit-risk (see [Appendix 5](#)).

From the Q2W expansion cohorts in Part C of the current study, AEs in the Broad Scope MedDRA Anaphylactic Reaction SMQ with onset within 2 days after sequential dosing of nivolumab 240 mg combined with BMS-986016 80 mg were reported in 14% of treated subjects. In Part D1-Q4W, if

the observed rate of these events is equal to 14% among 75 treated subjects in each arm, then the 95% CI for the difference in rates between arms will be (-11.1%, 11.1%) (see [Appendix 5](#)).

Table 8.1.4.2-1 shows the precision that the sample size of 75 treated subjects per arm in Part D1-Q4W and 150 treated subjects each in Part D1-Q2W and Part D1-Q4W dosing will provide for estimating rates and rate differences between the treatment arms under different assumed observed rates. Enrollment and randomization across treatment arms Part D1 BMS-986016 160 mg + nivolumab 480 mg Q4W coadministration and Part D1 BMS-986016 160 mg + nivolumab 480 mg Q4W FDC may continue until the following criteria are met: 90 efficacy-evaluable LAG-3-positive subjects have been treated, 60 efficacy-evaluable LAG-3-positive and BRAF wild-type subjects have been treated, and 60 efficacy-evaluable LAG-3-positive and ipilimumab pretreated subjects have been treated.

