## **1.3 Objectives**

### **1.3.1 Primary Objectives**

Parts A and B:

The primary objective of Parts A and B is to determine the safety, tolerability, dose-limiting toxicities (DLTs), and MTD of BMS-986016 administered alone and in combination with nivolumab in subjects with advanced solid tumors.

Part A1:

The primary objective of BMS-986016 monotherapy cohort expansion is to gather additional safety, tolerability, and preliminary efficacy information of BMS-986016 monotherapy.

Part C:

The primary objective is to further establish adequate safety and tolerability of BMS-986016 in combination with nivolumab administered sequentially.

The coprimary objective in Dose Expansion Part C is to investigate the preliminary efficacy of BMS-986016 in combination with nivolumab as measured by ORR, DCR, and DOR in multiple solid tumor types.

Part D:

The primary objective in Part D is to assess safety and tolerability of a more convenient dosing regimen (ie, coadministration and Q4W dosing interval).

Part D1-Q2W: The coprimary objective in Part D1-Q2W is to demonstrate preliminary clinical evidence of the treatment effect, measured by ORR, as determined by Blinded Independent Central Review (BICR) using Response Evaluation Criteria in Solid Tumors (RECIST) version 1.1, that may represent substantial improvement over available therapies in advanced melanoma subjects with LAG-3 expression who progressed while on anti-PD-1 antibody therapies.

Part D1-Q4W: The primary objective in Part D1-Q4W is to evaluate the difference in safety of coadministration relative to FDC as measured by the incidence of adverse events (AEs) in the Broad Scope Medical Dictionary for Regulatory Activities (MedDRA) Anaphylactic Reaction Standardized MedDRA Query (SMQ) occurring within 2 days after dosing in advanced melanoma subjects who progressed while on anti-PD-1 antibody therapies (see [Appendix 5](#)).

Part D1-Q4W: The coprimary objective in Part D1-Q4W is to confirm with Q4W dosing of BMS-986016 160 mg in combination with nivolumab 480 mg the safety of the Q2W dosing of BMS-986016 80 mg in combination with nivolumab 240 mg in advanced melanoma subjects who progressed while on anti-PD-1 antibody therapies.

Part E:

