Adolescents (12 to < 18 years of age) weighing less than 40 kg will be dosed based on weight (1 mg/kg BMS-986016 and 3 mg/kg nivolumab Q2W, 2 mg/kg BMS-986016 and 6 mg/kg nivolumab Q4W, or 6 mg/kg BMS-986016 and 6 mg/kg nivolumab Q4W. In Parts C, D, and E, Q4W dosing, BMS-986016 and nivolumab will be administered on Days 1 and 29 of each treatment cycle; visits will occur every 2 weeks to assess safety for the first cycle of treatment, and thereafter visits will only be on Day 1 and Day 29 of each subsequent cycle. [REDACTED]

Tumor

response will be evaluated using RECIST v1.1.

Subjects will be allowed to continue study therapy until the first occurrence of either 1) PD, 2) clinical deterioration, and/or 3) meeting other criteria for discontinuation. Refer to [Section 3.5](#) for additional details. Treatment beyond progression should be considered in select participants with initial RECIST v1.1-defined PD who are receiving clinical benefit as assessed by the Investigator, tolerating treatment, and meeting other criteria specified in [Section 4.3.4](#). Follow-up imaging should be obtained to confirm progression where appropriate (see [Section 5.1](#)). Subjects who discontinue treatment will enter a 135-day **Clinical Follow-up** period.

After completion of the Clinical Follow-up period, subjects enter the **Survival Follow-up** period. During this period, clinic visits or telephone contact every 12 weeks will be performed to assess survival status. Survival follow-up visits will be scheduled based on the last clinical follow-up visit. **Diagnostic imaging must be performed every 8 weeks until disease progression. For subjects who discontinue treatment at the Investigator's discretion with a CR, PR, or stable disease (SD) by RECIST v1.1, imaging must be performed every 12 weeks until disease progression.** The duration of this period may continue for up to 5 years from the first dose.

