**Table 5.1-2: On-treatment Procedural Outline for Q2W and Q4W BMS-986016/Nivolumab Treatment Regimens Parts A Through E**

Procedure	Treatment Cycles					Notes
	Day 1	Day 15	Day 29	Day 43	Day 50-56 a	
Visit Window for Q2W	± 2 days	± 2 days	± 2 days	± 2 days		
Visit Window for Q4W	± 3 days	± 3 days	± 3 days	± 3 days		
Study Drug Administration	Details regarding preparation and administration are provided in site training materials. c					
Parts A, A1, B, and C: BMS-986016 administration	X	X	X	X		Use vials assigned per IVRS: approximately 60-minute infusion.
Parts B and C Q2W: Nivolumab (BMS-936558) administration	X See Notes	X See Notes	X See Notes	X See Notes		Use vials assigned per IVRS. Nivolumab is administered ONLY for those subjects enrolled in Part B and Part C. Combination therapy with nivolumab and BMS-986016 will be administered as sequential infusions (Parts B and C). In Part C, nivolumab infusion will be administered over approximately 30 minutes.
Parts B and C Q4W: Nivolumab BMS-936558 and BMS-986016 administration	X See Notes		X See Notes			Combination therapy with nivolumab and BMS-986016 will be administered as sequential infusions. The nivolumab infusion will be administered over approximately 30 minutes and BMS-986016 over approximately 60 minutes. Study visits will occur Q2W (Day 1, 15, 29, 43) to assess safety for the first 3 cycles of treatment , and thereafter visits will only be on Day 1 and Day 29 of each subsequent cycle for Part B subjects. For Part C, study visits will occur Q2W (Day 1, 15, 29, 43) to assess safety for the first cycle of treatment , and thereafter visits will only be on Day 1 and Day 29 of each subsequent cycle.
Part D1 Q2W: Nivolumab BMS-936558 and BMS- 986016 coadministration	X See Notes	X See Notes	X See Notes	X See Notes		Combination therapy with nivolumab and BMS-986016 will be coadministered in a single IV bag over approximately 60 minutes.

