**Table 8.1.4.2-1: 95% CI for Rate Differences When Observed in 75 Subjects per Arm and 150 Subjects per Dosing Regimen**

75 Subjects per Arm		
Coadministration Arm	Fixed Dose Combination Arm	Rate Difference (95% CI)
14%	14%	0% (-11.1%, 11.1%)
14%	12%	2% (-8.8%, 12.8%)
16%	14%	2% (-9.4%, 13.4%)
18%	16%	2% (-10%, 14%)
20%	18%	2% (-10.6%, 14.6%)
150 Subjects Each in Part D1-Q4W and Part D1-Q2W		
Q2W	Q4W	Rate Difference (95% CI)
14%	14%	0% (-7.9%, 7.9%)
14%	12%	2% (-5.6%, 9.6%)
16%	14%	2% (-6.1%, 10.1%)
18%	16%	2% (-6.5%, 10.5%)
20%	18%	2% (-6.9%, 10.9%)

Also, with 75 subjects per arm, there is a 99% probability that the 95% CI for the geometric mean ratio of Cmax of FDC to coadministration is wholly contained within [0.8, 1.25]. log(Cmax) is assumed to follow a normal distribution and, with intrasubject coefficients of variation, is assumed to be no greater than 30%.

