The primary endpoint in Part D1-Q4W of the study is the incidence of AEs in the Broad Scope MedDRA Anaphylactic Reaction SMQ occurring within 2 days after dosing. This incidence rate is defined as number of subjects who experienced at least 1 AE in the Broad Scope MedDRA Anaphylactic Reaction SMQ with onset on the day of or within 2 days after any study therapy infusion divided by number of treated subjects. The terms included in the MedDRA Anaphylactic Reaction SMQ based on the most current MedDRA version will be listed in the statistical analysis plan (see [Appendix 5](#)).

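### Does counting reactions after any infusion make the Q2W versus Q4W safety comparison in Part D1 unfair, since Q2W has twice as many infusions?

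*Combined protocol and SAP*

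**What the plan says.** Section 1.3.1 gives Part D1-Q4W two safety aims. The first compares coadministration with the fixed-dose combination (FDC) on Broad Scope SMQ events. The second, a coprimary objective, is to "confirm with Q4W dosing of BMS-986016 160 mg in combination with nivolumab 480 mg the safety of the Q2W dosing" and names no metric.

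Section 8.3.1 defines the Part D1-Q4W primary endpoint as a subject-level incidence: a subject counts once if a Broad Scope event occurs "with onset on the day of or within 2 days after any study therapy infusion divided by number of treated subjects".

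Section 8.1.4.2 sizes both comparisons for precision. For the second it refers to "150 treated subjects each in Part D1-Q2W and Part D1-Q4W dosing will provide for estimating rates and rate differences between the treatment arms", and the lower block of Table 8.1.4.2-1 is headed "150 Subjects Each in Part D1-Q4W and Part D1-Q2W". That block does not name its rate. The text just before it reports the 14% Broad Scope rate from the Part C Q2W cohorts, and 14% versus 14% is the block's first row, so reading it as the Section 8.3.1 incidence is a sound inference, though still an inference.

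On schedule, Section 3.1 states that for "Q4W dosing, BMS-986016 and nivolumab will be administered on Days 1 and 29 of each treatment cycle". Table 5.1-2 marks Days 1, 15, 29 and 43 for Part D1 Q2W. Cycles last 8 weeks on both schedules.

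Section 8.4.3 plans incidence by arm, the difference and 95% confidence intervals, all descriptive. It describes no first-infusion or per-infusion table.

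**The concern.** A subject on Q2W has twice as many chances per cycle to be counted. Each window covers 3 days (the infusion day and the next two), so Q2W has 3 × 4 = 12 window days in 56 and Q4W has 3 × 2 = 6. A lower Q4W rate could come from fewer windows alone. An equal rate could hide a higher risk at each Q4W infusion, and each Q4W infusion carries twice the amount of both drugs (160/480 mg against 80/240 mg). If the coprimary objective were about how well each infusion is tolerated, the planned contrast could mislead, and the size of the effect is not trivial beside the planned precision.

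**Working it through.** **1. The plan's own figures.** Inputs from Table 8.1.4.2-1: 14% in each group, n = 150 or 75 per group, 95% confidence. The unpooled Wald half-width is 1.96 × √[p₁(1−p₁)/n + p₂(1−p₂)/n].

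- n = 150: 1.96 × √(2 × 0.14 × 0.86/150) = 7.85 points (stated 7.9).
- n = 75: 1.96 × √(2 × 0.14 × 0.86/75) = 11.11 points (stated 11.1).

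The other eight rows also reproduce to the stated rounding.

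**2. What infusion count alone can do.** Assume 14% on Q2W, equal treatment time, and the same risk at the same-numbered infusion on both schedules. The documents do not report how events split between first and later infusions, so a range is needed. The cumulative hazard on Q2W is H = −ln(0.86) = 0.1508 over k infusions; Q4W has k/2.

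| Hazard on first infusion | Q4W rate | Gap from 14% |
|---|---|---|
| None, k = 4 | 1 − exp(−0.1508/3) = 4.9% | 9.1 points |
| Constant over infusions, any k | 1 − exp(−0.1508/2) = 7.3% | 6.7 points |
| Half, k = 4 to 24 | 9.6% to 10.5% | 4.4 to 3.5 points |
| All | 14.0% | 0 points |

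At 150 per regimen, the constant-risk gap of 6.7 points has a 95% CI of −0.2 to 13.7. Conversely, 14% on both schedules under constant risk implies a per-infusion risk on Q4W 1.96 to 1.99 times that on Q2W (3.7% versus 7.3% with one cycle; 0.63% versus 1.25% with six).

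**3. Whether that is an error.** The objective compares dosing schedules. The quantity that answers it is the chance that a patient treated on a schedule has such a reaction, and fewer infusions are one of the ways Q4W can differ. A regimen-level incidence should therefore include the effect of infusion count. Section 1.3.1 contains no objective on risk per infusion.

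**4. What rests on the contrast.** Section 1.2 states that no hypotheses are formally evaluated, and Section 8.4.3 makes the contrast descriptive. There is no margin to pass or fail. Section 8.3.1 also measures safety by AEs, SAEs, AEs leading to discontinuation, deaths and laboratory abnormalities; Section 8.3.2.5.1 adds Grade 3–5 AEs; and Section 8.4 summarises expansion safety by dose and dosing regimen. The coadministration versus FDC comparison has equal infusion schedules in both arms.

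**5. What a first-infusion table would add.** Expected Q2W subjects with an event after the first infusion, out of 150, under constant risk: 150 × 3.70% = 5.6 with k = 4, down to 150 × 0.63% = 0.9 with k = 24. With half the hazard on the first infusion it is 150 × 7.26% = 10.9; with all of it, 150 × 14% = 21. The table is thinnest where infusion count matters most. Extending it to the first two infusions would compare Days 1 and 15 with Days 1 and 29, which brings in a difference in time since treatment start.

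**The case for a change.** The strongest case for the concern is that a zero effect is unlikely. The Broad Scope list in Appendix 5 includes cough, dyspnoea, rash and pruritus. Section 1.5 names pruritus and rash among the most frequent drug-related AEs. Such events need not cluster at the first infusion, and the chance that one falls in a window rises with the number of windows. Section 1.1.9.4 predicts roughly 40% higher peak steady-state nivolumab concentrations with 480 mg Q4W, so tolerability of the larger infusion is a fair clinical question. The possible artefact, up to about 9 points, is as large as the half-widths in the 150-subject block (7.6 to 8.9 points). The data for a first-infusion table should already exist, since the 2-day window requires onset and infusion dates.

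This stands as a limit on interpretation: the any-infusion contrast, read alone, cannot separate risk per infusion from number of infusions. It does not stand as a fault. Section 1.1.9.4 judges that the predicted exposures do not put subjects at increased risk, and Section 1.4.1.4.2 reports no dose relationship for AEs in general. An extra table would answer a question the protocol does not pose, with few events in the case that matters, and would change no planned result. Enrolment closed on 30-Jul-2021 (Appendix 7), so it would also be a late addition.

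Two related facts have nothing to do with infusion count and do not strengthen the point. Q2W enrolment began before randomisation ("Prior to Revised Protocol 09, subjects are being enrolled into a single arm"), and the Q4W group pools two products ("Approximately 150 subjects will be randomized to the 2 treatment arms Part D1 BMS-986016 160 mg").

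**Conclusion.** The concern does not hold. The any-infusion incidence is a valid regimen-level measure, it fits the stated objective, and its planned precision is correctly calculated. Infusion count alone could move the Q2W minus Q4W difference by 0 to about 9.1 points. That range assumes 14% on Q2W (taken from sequential dosing in Part C, not from Part D1 coadministration), equal treatment time, and timing patterns from all risk on the first infusion to none. It reflects a real difference between the schedules and does not bias the question asked. The report should simply avoid reading similar regimen rates as evidence of similar risk per infusion. The conclusion rests on taking the lower block of Table 8.1.4.2-1 to refer to the Broad Scope incidence, and on the comparison staying descriptive. It would need another look if a claim about tolerability of each infusion were to be based on this contrast.
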